Appendix A Study Procedure Calendar

1.0 Background

Pediatric forearm fractures are extremely common, accounting for up to 40% of all pediatric fractures and consequently, the financial healthcare burden is large. The rate of displacement following closed reduction with casting/splinting of such fractures is high, varying between 21-39% (Meta-analysis Sengab). Consequences of fracture displacement include multiple adverse complications such as repeat sedation and fracture manipulation causing pain and distress, urgent or unplanned surgical interventions, and potentially malunion of the fracture. In addition to the morbidity of suboptimal fracture healing, there are significant functional consequences that could result due to fracture malunion. Previous studies have evaluated risk factors for forearm fracture displacement following closed reduction including initial displacement, cast index, and BMI however, little work has been done to evaluate the influence activity plays on the displacement/malunion of these fractures. As a result, this leads to inconsistent and nebulous recommendations provided to families regarding activity restrictions after closed treatment of fractures (i.e. non-surgical treatment). One can find significant variability in activity recommendations based on practices and individual provider preferences. Several studies have been conducted in other pediatric patient population to assess activity levels of children with various comorbidities. The purpose of this study is to evaluate the effect of activity on fracture displacement using and actigraph activity monitoring device. This device is externally applied and is an FDA approved activity monitoring devices with an extensive research background.

2.0 Rationale and Specific Aims

Rate of displacement following cast/splint application has been studied and varies between 21-39% based on the meta-analysis by Sengab et al. This randomized pilot study will include roughly 50-100 patients and will be completed in approximately 1 year with preliminary results available at that time. Between the 8 physicians and 4 nurse practitioners on staff within the pediatric orthopaedics department, approximately 20 patients weekly are seen who would meet eligibility for study participation. Assuming a 10% successful recruitment rate, it would require 6 months to recruit the desired number of participants. Eligible patients will be offered study inclusion during the initial outpatient clinic visit. These patients typically present to the clinic 3-7 days following injury.

The primary aim of this study is to determine whether activity influences loss of reduction of forearm fractures. Secondary aims of this study may provide insight to many other related questions as seen below:

- Does increased activity lead to more complications.
- Do instructions given to families influence activity level and do patients/families accurately report activity levels?
- Does activity level affect recovery length time of forearm fractures based on x-ray findings?

3.0 Animal Studies and Previous Human Studies

Multiple previous studies have investigated risk factors for loss of reduction. Previous studies have identified increased displacement at the time of injury and a cast index >0.8 as risk factors for loss of reduction. No studies have been conducted regarding the influence of activity on pediatric forearm fractures. Thousands of previous studies have used actigraph activity trackers, the monitoring device to be used in this proposed study, in the area of pediatric obesity, cardiology, and oncology, but no known prior study has used the device in pediatric orthopedic patients.

4.0 Inclusion/Exclusion Criteria

Included in the study will be patients ages 8-18 years old with fractures of radius and/or ulnar shaft or distal radius fracture. Specifically the following fractures will be included:

- Isolated Distal Radius Metaphyseal Fx (with or without ulna styloid)
- Distal Third (<4 cm from physis) Radius and Ulna fracture (i.e. without obvious physeal involvement)
- Insolated Radial Shaft Fracture (diaphyseal)
- Radial and Ulna Shaft Fracture (diaphyseal)

Exclusion Criteria include:

- Initial presentation >7 days from the time of injury
- Pathologic fracture
- Any patient with metabolic bone disease (ex. Osteoporosis, skeletal dysplasias)
- Any patient with known bone fragility condition (ex. Osteogenesis imperfecta)
- If operative treatment is required at initial presentation

5.0 Enrollment/Randomization

General inclusion/exclusion criteria will be used to determine patient eligibility. All eligible patients will be identified when they present to Vanderbilt's pediatric orthopedic clinic based on the clinicians interpretation of their presenting x-rays.

Consent is obtained during the office visit on paper or by REDCap econsent. Patients and families will be given as much time as they need to review the documents and ask questions. The patient consent process will be conducted using a REDCap-based electronic consent form or a paper consent form. The consent form has been developed in REDCap, a secure, web-based, HIPAA-compliant, data collection platform with a user management system allowing project owners to grant and control varying levels of access to data collection instruments and data (e.g. read only, de-identified-only data views) for other users.

If a patient decides to participate in the study, they will randomized to one of two groups: Group A and Group B. Patients will be randomly assigned to one of groups based on the date of enrollment. If the date of enrollment is an odd integer, they will be placed in Group A. If the date is an even integer, they will be placed in Group B.

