6.0 Study Procedures

The procedure studies will be as followed:

- Once non-operative management is deemed appropriate based on review of imaging and shared decision making with the family, eligible patients will be offered study participation during initial presentation at outpatient clinic visit (about 3-7 days post-injury). At the initial visit:
 - Standard or care X-rays will be reviewed
 - As part of standard of care a cast will be applied (or overwrapped with fiberglass)
 - Some participants will be provided an activity monitoring, based on availability, to be worn on the uninjured wrist or ankle consistent with manufacturers recommendations for the duration of casting treatment.
 - Participants will be randomized into restricted activity vs full activity groups and be read a respective standardized script regarding activity limitations. The same guidance will also be provided in the after visit summary (AVS).
 - Basic data will be collected including patient age, sex, BMI, initial displacement measurements, and other pertinent fracture characteristics easily obtainable from review of present radiographs.
- Patients will follow up at standard of care 1-2 week intervals for alignment checks. At these visits:
 - If the participants was provided a tracker, data from the monitoring devices will be imported with only a study id and date of birth to identify the patient. All data on the device will be deleted when information is imported.
 - Repeat standard of care x-rays will be obtained to assess for loss of reduction (defined as any change in angulation >10 degrees compared to initial reduction).
 - Incidence of complications such as unplanned cast changes, excessive skin irritation, cast wedging, loss of reduction, and operative management will be recorded.
 - For all enrolled patients, regardless of use of activity monitoring device, a validated Pediatric Activity Survey will be provided at follow-up appointments.
- Following all data collection, patient, survey, and activity tracker data will be analyzed

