12.0 Follow-up and Record Retention

The duration of this study will last until we have enrolled 100 patients and will continue 3-4 months after the last patient is enrolled to ensure fracture healing is complete and any potential complications are captured. No additional research related follow up visits are required as part of this proposed study. Patients will follow at routine intervals regardless of study participation. All study data will be maintained for 6 years following study completion. Following this 6 year period, the Redcap database will be archived, electronic files will be permanently deleted, and all physical study forms will be disposed of in shred-it confidentiality bins provided by VUMC.

Appendices:

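### Allocation by enrolment date leaves initial displacement, a risk factor the protocol names and records, to chance: a modest but avoidable loss of precision

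*Protocol*

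**What the plan says.** Section 5.0 fixes the allocation rule: "Patients will be randomly assigned to one of groups based on the date of enrollment". It then spells the rule out: "If the date of enrollment is an odd integer, they will be placed in Group A", and even dates go to Group B. No stratification, blocking or minimisation is mentioned.

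On prognosis, Section 3.0 says: "Previous studies have identified increased displacement at the time of injury and a cast index >0.8 as risk factors for loss of reduction". Section 4.0 admits four fracture categories, from isolated distal radius metaphyseal fractures to shaft fractures of both bones. For the initial visit, at which children are also assigned to their group, Section 6.0 says: "Basic data will be collected including patient age, sex, BMI, initial displacement measurements, and other pertinent fracture characteristics".

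On size, Section 2.0 says: "This randomized pilot study will include roughly 50-100 patients". Section 12.0 says: "The duration of this study will last until we have enrolled 100 patients". Section 10.0 names no analysis model.

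**The concern.** The protocol regards displacement as prognostic, and it has the measurement to hand when the child is allocated. Its allocation rule cannot use that measurement, because date parity takes no input other than the calendar. Even if staff follow the rule faithfully, the mix of more and less displaced fractures in each arm is left to chance, in a study small enough for visible imbalance to be common.

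Two things are at stake. If displacement is ignored, the arm difference is estimated less precisely than the collected data allow. And if one arm visibly holds more displaced fractures, readers may attribute the primary result to displacement and not to activity.

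**Working it through.** **The plan's own figure.** The protocol states no power or precision calculation. Its only supporting arithmetic is recruitment in Section 2.0: 20 eligible per week x 10% = 2 per week, and 2 x 26 weeks = 52. This matches the lower end of the range (50 takes 25 weeks) but not 100 (50 weeks). Both sizes are therefore carried below.

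**Inputs from the protocol.** N = 50 or 100. The outcome rate is 21-39% (Section 2.0), midpoint 30%.

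**Assumed inputs.** Equal allocation; a share q of children with high displacement of 30% or 50%; loss-of-reduction risks p0 (low displacement) and p1 (high displacement) chosen to give an overall risk p of about 30%. The date rule is treated as a fair coin per child. This ignores the fact that children enrolled on the same day share an arm.

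**Step 1: chance imbalance.** With n per arm, the SD of the between-arm difference in q is sqrt(2q(1-q)/n).

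- q = 0.5: sqrt(0.5/25) = 0.141 and sqrt(0.5/50) = 0.100. A 20-point gap is 1.41 or 2.00 SDs, so its probability is 0.157 or 0.046.
- Simulation (40,000 trials per scenario, q of 0.3 or 0.5) gives 13-17% at N = 50 and 3-5% at N = 100. A gap of 10 points or more occurs in 45-49% and 27-33%.

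**Step 2: precision.** The share of outcome variance explained by displacement is q(1-q)(p1-p0)²/(p(1-p)). For q = 0.5 and risks of 15% and 45%, it is 0.25 x 0.09/0.21 = 0.107. The expected cut in the standard error is 1 - sqrt(1 - 0.107) = 5.5%.

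The simulation compared the SD of the risk difference under three approaches: no stratification with a crude comparison; no stratification with Mantel-Haenszel adjustment for displacement; and allocation balanced within displacement strata.

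| N | q | p0 / p1 | Crude | Adjusted only | Balanced | SE cut by balancing |
|---|---|---|---|---|---|---|
| 50 | 0.5 | 20% / 40% | 0.1304 | 0.1284 | 0.1268 | 2.8% |
| 50 | 0.5 | 15% / 45% | 0.1307 | 0.1249 | 0.1231 | 5.8% |
| 50 | 0.3 | 20% / 50% | 0.1295 | 0.1245 | 0.1216 | 6.1% |
| 50 | 0.5 | 10% / 50% | 0.1311 | 0.1188 | 0.1170 | 10.8% |
| 100 | 0.5 | 20% / 40% | 0.0919 | 0.0901 | 0.0899 | 2.2% |
| 100 | 0.5 | 15% / 45% | 0.0925 | 0.0878 | 0.0868 | 6.2% |
| 100 | 0.3 | 20% / 50% | 0.0915 | 0.0872 | 0.0864 | 5.6% |
| 100 | 0.5 | 10% / 50% | 0.0926 | 0.0835 | 0.0827 | 10.7% |

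The simulated cuts slightly exceed the formula partly because coin-flip allocation also leaves the arm sizes unequal. In variance terms, balancing saves 5-20% at N = 50 and 4-20% at N = 100. Adjustment alone saves 3-18% and 4-19%.

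**Step 3: scale.** At an overall risk of 30%, the 95% half-width is 1.96 x sqrt(2 x 0.21/n): 25 points for n = 25 and 18 points for n = 50. In the 15% / 45% scenario, balancing moves it from 1.96 x 0.1307 = 26 to 1.96 x 0.1231 = 24 points at N = 50, and from 18 to 17 points at N = 100. By comparison, going from 50 to 100 children cuts the standard error by 1 - 1/sqrt(2) = 29%.

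**Step 4: effect of one bad draw.** A 20-point imbalance shifts the crude risk difference by 0.20 x (p1-p0), which is 4 to 8 points here. The standard error is about 13 points at N = 50 and 9 at N = 100, so the shift is always less than one standard error.

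**The case against.** The strongest reply is that unstratified allocation is an accepted choice for a small pilot, that ordinary confidence intervals already allow for chance imbalance, and that adjustment for displacement is commonly settled in a statistical analysis plan, which may exist but is not shown. Much of this stands. Adjustment alone recovers most of the gain, and at N = 100 stratified allocation adds little beyond it. The protocol cannot be faulted for leaving the model to another document. What does not fall away is the allocation rule. It is fixed in Section 5.0, a later analysis plan cannot change it, and it cannot accommodate a prognostic factor.

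Three stronger readings are tempting, and the documents do not support them.

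- *A reader might infer that the comparison is biased because displacement is left to chance.* Chance imbalance widens uncertainty; it is not bias. The predictability of a date rule, which can let enrolment be steered by arm, is a separate and graver matter that does not depend on stratification.
- *A reader might infer that missing stratification is the main reason the result will be imprecise.* Step 3 shows that the sample size dominates.
- *A reader might infer that the trial mixes reduced and unreduced fractures and should stratify on that.* Section 4.0 neither requires nor excludes a reduction, and the outcome in Section 6.0 is measured against an initial reduction. Reduction status is not named as a risk factor, and the protocol gives no outcome rate for unreduced fractures. The factor it does name is displacement.

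**Conclusion.** The point holds as a low-cost improvement, not as a flaw that undermines the trial. The date rule cannot balance a risk factor that the protocol names and records at the visit where allocation occurs. The cost of ignoring displacement is about 2-11% of the standard error, with an imbalance of 20 points or more in roughly 13-17% of trials at N = 50 or 3-5% at N = 100. If the 100 in Section 12.0 governs, the lower figures apply.

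These sizes depend on assumed values: 30-50% of children with high displacement and differences in risk of 20 to 40 points between displacement groups. The protocol supplies neither. A weaker predictor would make the loss smaller. The simulated gain also assumes near-perfect balance within strata, so it is close to the most that stratification could deliver.

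**What to change.** In Section 5.0, replace the date rule with a concealed randomisation list, for example held in REDCap, which the trial already uses for consent and data collection. Stratify it by one two-level factor: initial displacement above or below a cut-off that the investigators set before enrolment starts. With 50-100 children, one factor is enough. State which radiograph the measurement comes from, and require it to be entered before the arm is revealed.

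Adjust the arm comparison for the baseline displacement already collected. This is needed even with stratified allocation, because an interval that ignores the strata would not show the precision gained.

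The cost is one stratification field and one covariate, with no extra visits, measurements or patients. The change is best made together with replacing the date rule on grounds of predictability. If allocation were left as it is, adjustment alone would still recover most of the precision, but it would not address predictability.

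### The arm is set by odd or even enrolment date, so it is known before eligibility is judged and consent sought; the trial is called randomized but is open to selection bias

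*Protocol*

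**What the plan says.** Protocol section 5.0 states: "Patients will be randomly assigned to one of groups based on the date of enrollment". The rule follows: "If the date of enrollment is an odd integer, they will be placed in Group A" and "If the date is an even integer, they will be placed in Group B". Group A receives the restricted-activity script and Group B the activity-as-tolerated script (Appendix A).

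The same section makes eligibility a judgement by the treating clinician at the clinic: "All eligible patients will be identified when they present to Vanderbilt's pediatric orthopedic clinic based on the clinicians interpretation of their presenting x-rays". Section 6.0 adds a second judgement before the offer: "Once non-operative management is deemed appropriate based on review of imaging and shared decision making with the family, eligible patients will be offered study participation". Section 4.0 excludes patients who need an operation at presentation, so this second judgement is part of eligibility. On consent, section 5.0 says: "Consent is obtained during the office visit on paper or by REDCap econsent".

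Section 2.0 calls the study a randomized pilot of roughly 50 to 100 patients, section 6.0 repeats the term, and both scripts in Appendix A tell families that the child has been randomized. The Protocol describes no random sequence, no concealment and no separate person who holds the allocation.

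**The concern.** Date parity is a deterministic rule, and everyone in the clinic can apply it. A clinician who looks at the calendar in the morning knows which arm every patient enrolled that day will receive. Randomization protects a comparison only if those who decide who enters cannot foresee the assignment. Here they can, and they also see prognosis: section 3.0 names initial displacement as a risk factor for loss of reduction, and displacement is visible on the presenting film.

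Section 1.0 says that activity advice varies with the preferences of individual providers, so clinicians do not come to the study without views. One who is uneasy about activity could, without any bad intent, be slower to offer the study for an unstable-looking fracture on an even date. Section 3.0 also names the cast index as a risk factor. The Protocol does not fix whether the cast is applied before or after assignment, so the casting itself could be done with the arm known.

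If this happens, the arms differ in baseline risk and a difference in loss of reduction cannot be attributed to the advice. The arm comparison is the part of the study that randomization is meant to protect. Measured activity, from surveys in all patients and trackers in some, is not randomized.

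**Working it through.** The Protocol gives no figure to reproduce here. The check covers the mechanism and then illustrates its possible size.

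**1. Predictability.** Under the stated rule, P(Group A | odd date) = 1 and P(Group B | even date) = 1, so the next arm is guessed correctly with probability 1.00. Under concealed simple 1:1 randomization the probability is 0.50.

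**2. Order of events.** The date is fixed before the visit begins. Reading the x-rays, deciding on non-operative care, offering the study and taking consent (sections 5.0 and 6.0) all come after it. Each is a point at which entry can depend on the arm.

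**3. Room for selection.** Section 2.0 expects about 20 eligible patients a week and plans on the basis of "Assuming a 10% successful recruitment rate". That gives 20 × 0.10 = 2 enrolled and 18 not enrolled per week. With so many eligible patients outside the trial, selection by arm would be hard to detect.

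**4. Bias from selective enrolment, no true effect.** Assume two equally common strata with risks lo and hi, averaging 30%. Enrolment is even-handed on odd dates. On even dates a higher-risk patient is r times as likely to be enrolled as a lower-risk one.

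- Group A risk = (lo + hi)/2 = 0.30
- Group B risk = (lo + r × hi)/(1 + r)

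| Strata | r | Group B risk | Spurious difference, B − A |
|---|---|---|---|
| 21% / 39% | 0.5 | (0.21 + 0.195)/1.5 = 27.0% | −3.0 points |
| 21% / 39% | 0.25 | (0.21 + 0.0975)/1.25 = 24.6% | −5.4 points |
| 10% / 50% | 0.5 | (0.10 + 0.25)/1.5 = 23.3% | −6.7 points |
| 10% / 50% | 0.25 | (0.10 + 0.125)/1.25 = 18.0% | −12.0 points |

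The values 21% and 39% are the ends of the displacement range in section 2.0, used here as stratum risks by assumption. The 10%/50% pair and both values of r are assumptions.

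**5. Effect on a test.** This is a second illustration, with strata of 21% and 39% and no true effect, where the share of high-risk patients is m in one arm and 1 − m in the other. Each arm's risk is 0.21 + 0.18 × share. For a two-sided 5% pooled two-proportion z-test with n per arm and d the difference in risk:

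- SE0 = √(2 p̄(1 − p̄)/n)
- SE1 = √(p1(1 − p1)/n + p2(1 − p2)/n)
- rejection rate = Φ((d − 1.96 SE0)/SE1) + Φ((−d − 1.96 SE0)/SE1)

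| High-risk share | Risks | d | 25 per arm | 50 per arm |
|---|---|---|---|---|
| 40% vs 60% | 28.2% vs 31.8% | 3.6 points | 5.9% | 6.8% |
| 30% vs 70% | 26.4% vs 33.6% | 7.2 points | 8.5% | 12.2% |
| 20% vs 80% | 24.6% vs 35.4% | 10.8 points | 13.1% | 21.6% |

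The arm sizes are half of the planned 50 and 100 patients. The nominal rate is 5%.

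**6. Balance in numbers.** In a 365-day year, seven months have 16 odd dates, four have 15 and February has 14: 7 × 16 + 4 × 15 + 14 = 186 odd dates, leaving 179 even (51.0% odd). This is minor. The defect is predictability, not unequal numbers.

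**The case against.** The strongest reply is that the text shows opportunity, not selection. The Protocol says that all eligible patients will be identified and that eligible patients will be offered the study, so on paper nobody is licensed to choose whom to approach. The 10% is a planning assumption with no stated reason; refusal by families would explain it as well as selective approach. Consent is placed at the office visit, so moving it to a preferred date is not described, although families may take as long as they need. At about 2 enrolments a week, same-day clustering hardly matters. A film reader could infer the arm only if told the enrolment date. The illustrations rest on invented selection ratios. In the mildest case, 3 points is about a quarter to a third of a standard error (0.130 at 25 per arm, 0.092 at 50 per arm, from √(2 × 0.3 × 0.7/n)), which is small for a pilot. Finally, age, sex, BMI and initial displacement are recorded and can be adjusted for.

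Most of these limits are fair, and they bear on how large the bias would be. They leave the core untouched. An instruction to offer the study to all eligible patients does not help when eligibility is itself a judgement made with the arm known. Adjustment handles only what is measured, and 50 to 100 patients support little of it. Calling the study a pilot does not excuse the rule either: section 2.0 makes the influence of activity on loss of reduction the primary aim, and a secondary aim asks whether the instructions change activity, which is a direct comparison of the arms.

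**Conclusion.** The concern holds. Section 5.0 calls the assignment random and then prescribes a rule with no chance in it and no possibility of concealment. No other section repairs this, and a statistical analysis plan could not restore concealment after the fact.

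The certain part is that the arm is predictable with probability 1.00 at the time of every entry decision. The size is conditional on behaviour that the Protocol cannot reveal. Under the assumed strata and selection ratios, a spurious difference of 3 to 12 percentage points could appear with no true effect. Under the separate case-mix illustration, the false-positive rate would be 5.9% to 21.6% instead of 5%. These figures show what the rule permits and are not forecasts. Because the defect cannot be repaired once patients are enrolled, it must be fixed in the Protocol.

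**What to change.** Delete the odd/even sentences in section 5.0. Replace them with a computer-generated 1:1 list in permuted blocks of varying size, prepared by someone not involved in enrolment. Load it in REDCap and reveal the arm only after eligibility is confirmed and consent is recorded, and preferably after the cast is on. State this order in section 6.0, so that entry and casting are both settled before the arm is known.

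Stratification is optional and not needed for concealment. If it is wanted, fracture site (distal or shaft) is a reasonable single factor for 50 to 100 patients; whether the fracture was reduced could be added if feasible.

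If the date rule is kept, the study should be called quasi-randomized throughout, and the scripts in Appendix A should no longer tell families that the child has been randomized. That corrects the label but leaves the bias.

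The cost is a protocol amendment and a short set-up. The Protocol already uses REDCap for consent and data; that its randomization function is available locally is an assumption to confirm. There are no extra patients, visits or staff. Enrolment takes one more step, and both scripts must be on hand every day.
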